5.0 TREATMENT PLAN

5.1 Accrual scheme

As outlined in Section 9.0 (Statistical Considerations), a total of 16 subjects will be treated with complete surgical resection and a minimum of 2 courses of protocol treatment. This may mean that additional subjects will need to be entered to account for subjects enrolled into the study and unable to

receive the complete resection and/or entered into the study and unable to receive the first two courses of protocol treatment. Accrual will be stratified to ensure that 8 evaluable subjects are entered into each arm and have received both surgery and 2 courses of study therapy. Stratification will also attempt to enroll similar numbers of subjects requiring extensive surgery and non-extensive surgery (see Section 4.4.8) into each of the treatment groups. The detailed clinical and laboratory monitoring is outlined in protocol Section 7.0 (Study Parameters), Tables 5 and 7.

5.2 Surgical resection of all detectable melanoma

5.2.1 Treatment Group A

Subjects in Group A will have complete surgical resection of all detectable melanoma following Course 1 of hu14.18-IL2. Surgical resection will be scheduled for 7-14 days following the completion of the first 3-day course of therapy (i.e., days 10-17) in order to insure reversal of hu14.18-IL2 toxicities prior to the surgery. These ranges will allow enough flexibility so that the appropriate surgical subspecialist will be available to perform the resection.

Once the subject has recovered from the surgery (2-4 weeks, depending upon the nature of surgery (Section 4.4.8), the subject will begin Course 2 of treatment. Decisions regarding whether a subject has recovered sufficiently from surgery to begin Course 2 of treatment will be left to the discretion of the treating physician(s). To aid in this decision, laboratory tests may be ordered as warranted clinically, but no specific tests are required for this assessment. Subjects undergoing “extensive surgery” (see Section 4.4.8) will not begin Course 2 of study treatment until at least 21 days after surgery. Subjects undergoing “non-extensive surgery” will not begin Course 2 of study treatment until at least 14 days after surgery (see Section 4.4.8). No course of hu14.18-IL2 therapy will be administered sooner than 4 weeks after day 1 of the prior course of hu14.18-IL2 therapy. Subjects will receive a total of 3 courses of treatment as described in Section 5.3.

5.2.2 Treatment Group B

Subjects in Group B will have complete surgical resection of all detectable melanoma upon study entry, prior to Course 1 of hu14.18-IL2. Once the subject has recovered from the surgery (2-4 weeks, depending upon the nature of surgery (Section 4.4.8), the subject will begin Course 1 of treatment. Decisions regarding whether a subject has recovered sufficiently from surgery to begin Course 1 of treatment will be left to the discretion of the treating physician(s). To aid in this decision, laboratory tests may be ordered as warranted clinically, but no specific tests are required for this assessment. Subjects undergoing “extensive surgery” (see Section 4.4.8) will not begin Course 1 of study treatment until at least 21 days after surgery. Subjects undergoing “non-extensive surgery” will not begin Course 1 of study treatment until at least 14 days after surgery (see Section 4.4.8). No course of hu14.18-IL2 therapy will be administered sooner than 4 weeks after day 1 of the prior course of hu14.18-IL2 therapy. Subjects will receive a total of 3 courses of treatment as described in Section 5.3.

5.2.3 Surgical guidelines

The surgical management of subjects in this study will vary depending on the site(s) of tumor. Two broad categories of subjects are eligible: 1) subjects with loco-regional recurrence of resected stage III disease; and 2) subjects with resectable stage IV disease. All subjects will be assessed by a surgical oncologist prior to consideration for this study. Three clinical criteria must be met: the subject must be thought to have completely resectable disease; the disease must be in 3 or fewer sites; and the subject must be able to tolerate a resective surgical procedure. Subjects with loco-regional recurrence typically have either subcutaneous in transit disease, or a nodal recurrence in the

draining nodal basin. A nodal basin recurrence will be scored as one site, even if multiple nodes are positive. “Clustered” subcutaneous and/or cutaneous lesions that can be removed in a single surgical excision will be scored as one site, even if multiple subcutaneous and/or cutaneous lesions are present. If at the time of the preoperative assessment, the oncologic surgeon believes the lesion(s) can be resected completely with negative surgical margins, the subjects will undergo surgical resection. In the event that the pathologic margins demonstrate microscopic residual disease, patients will remain on protocol provided that their evaluation following course two shows no radiographically or clinically evident disease.

Subjects with stage IV disease may have visceral disease, cutaneous disease, and/or subcutaneous disease. Subjects with subcutaneous disease will undergo resection if the clinical criteria outlined above are met. Subjects with visceral disease have significantly higher operative morbidity. The most common sites of resectable visceral disease are the small bowel and lung. Most subjects with isolated visceral disease are offered operative intervention as a standard of care. If 3 or fewer sites of disease are found, they will undergo resection. If more than 3 sites are found, based on the above guidelines, patients will undergo intervention based on their symptoms and the best clinical judgment of the treating oncologist and surgeon, but will be ineligible for this study. Eligibility decisions, based on clinical resectability, will be made by the surgical oncologist.

5.3 Treatment schedule and dose

The treatment regimens for each study group are summarized below (see also Schema above):

- **Group A:** one course of IC, followed by surgical resection, followed by two courses of IC
- **Group B:** surgical resection, followed by three courses of IC

Guidelines for initiation of therapy, following the surgical resection (Course 1 for subjects randomized to Group B and Course 2 for subjects randomized Group A) are provided in Section 5.2. Treatment Courses 1-3 (for Group B) and Courses 2-3 (for Group A) will be repeated every 28 days (+/- 7 days to allow for scheduling constraints) at the same dose, provided that there is no dose limiting toxicity (see Section 5.4) or non-DLT toxicity the treating physician feels warrants dose reduction. Subjects can receive a maximum of 3 courses of therapy. Hu14.18-IL2 will be given on days 1, 2, and 3 of each course of therapy as a 4-hour continuous IV infusion at a daily dose of 6 mg/m²/d. (Note: given the relatively short supply of hu14.18-IL2 available, before each subject begins study treatment, we will confirm with the hospital pharmacy that there is sufficient material available in our pharmacy for that subject to receive all planned doses.) The infusions will be stopped only under the following circumstances: if dose-limiting toxicity is noted (see Section 5.4.4), if the treating physician deems it in the subject’s best interest to discontinue the infusion for a significant, but non-DLT toxicity, when blood draws are needed, when other intravenous medications must be administered, if adequate intravenous access is lost (and a new IV must be placed), and/or if a subject decides to withdraw from the study.

5.3.1 Subsequent Courses:

5.3.1.1 Subjects may continue treatment if all toxicities have recovered to \leq Grade 1 or the subject meets initial eligibility criteria, and there is no symptomatic disease progression (Section 6.0)

5.3.1.2 Course 3 will be administered only to subjects with a documented complete clinical response (i.e., no radiological or clinical evidence of disease) following Course 2 of treatment (see details regarding statistical evaluation in Section 9.5) provided that all toxicity has resolved to \leq Grade 1 or meets initial eligibility criteria.

5.3.1.3 Subjects not showing CR following surgical resection and 2 courses of study therapy (i.e., at the evaluation following Course 2) will be considered to have progressive disease and will not be eligible for subsequent treatment. In addition, their position in the study group will be filled with a new, randomly assigned subject (see Section 9.3.2 for details). There is always the possibility that clinical or radiographic criteria indicating potential residual melanoma at this time could actually reflect post-operative changes in x-rays or scans or clinical exams, and may not necessarily reflect true progressive/residual disease. Thus, any subject that does not appear to be in CR at this time should have any site of potential recurrent, residual or progressive disease biopsied if that site is considered safely amenable to biopsy (see Section 6.0). In the interest of safety, the biopsy will be performed at least 7 days following the completion of hu14.18-IL2 and as soon after the suspect radiographic data were obtained and/or physical findings were identified (i.e., preferably within 14 days, with efforts not to exceed 21 days). If this biopsy is not consistent with melanoma, the subject may continue with Course 3 of study treatment. Treatment may be delayed to allow for recovery from the biopsy procedure (i.e., preferably no more than a 1-week delay but absolutely not longer than 3 weeks). Decisions related to the duration of time needed to recover from the biopsy, prior to resuming treatment, will be left to the discretion of the treating physician(s). To aid in this decision, laboratory tests may be ordered as warranted clinically, but no specific tests or evaluations are required for this assessment.

In the event that the area of questionable residual disease is not considered safely amenable to biopsy (for example, a small pulmonary nodule that may reflect old infection, atelectasis, or post operative scarring), and is considered potentially to reflect non-malignant post-operative change, the subject may continue with protocol treatment, and will be considered an evaluable subject for this study.

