² Hu14.18-IL2 will be administered as a 4-hour IV infusion on days 1, 2, and 3 in the first week of each treatment cycle. Each treatment cycle is 4 weeks (+/- 7 days). Subjects in this study will be administered 6 mg/m²/d of hu14.18-IL2, a dose corresponding to one dose below the maximal tolerated dose (MTD) as determined in our completed Phase I study.

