1.5 Study rationale

1.5.1 Rationale for schedule of administration

Administration of hu14.18-IL2

Daily administration of hu14.18-IL2 is indicated based on preclinical and clinical findings demonstrating a substantial clearance of the IC protein from the circulation within a day (approximately 10% or less remaining after 24 hours) ([name], unpublished). In this study, a 3-day treatment cycle has been chosen to provide repeat, prolonged tumor exposure to hu14.18-IL2. The dose and schedule for this study (6.0 mg/m² given daily for 3 days every 4 weeks) was determined by our recently completed Phase I study of hu14.18-IL2 (see section 1.5.2.1).

A consecutive 3-day administration schedule was originally chosen for our Phase I study because of concern that a greater than 3 consecutive day administration would result in higher levels of neutralizing antibodies. This was based on preclinical testing with cross-species administration, where daily infusion of the IC protein was found to result in the production of neutralizing antibodies beginning on Day 4. Preliminary data from our laboratory, however, indicates that neutralizing antibodies appear at approximately Day 8 of our Phase I study,

therefore a 3-day administration schedule would be expected to provide a prolonged tumor exposure to hu14.18-IL2 without interference of substantial levels of neutralizing antibodies.

The 3-day administration schedule will be repeated on a 4-week interval, allowing for stable and responding subjects to continue receiving potentially clinically beneficial treatment. In addition, this dosing schedule will allow, in those subjects that have generated any antibody to hu14.18-IL2, the determination of neutralizing capabilities of these antibodies upon re-exposure to hu14.18-IL2. While the preclinical data reflect a cross-species immunogenic effect, a potential anti-idiotypic response is still possible, albeit at a much reduced level, and has in fact been observed in some patients in the Phase I trials ([name] et al., in preparation).

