5.4.4.1 Dose-reduction plan for hu14.18-IL2

For toxicity associated with hu14.18-IL2, there must also be consideration of the schedule of administration. If this toxicity occurs on day 1 or 2 of any course, treatment can be resumed during that same course (i.e., on day 2 or 3) at 50% of the starting dose only if the toxicity has improved to meet eligibility criteria in time to give the day 2 or day 3 dose on schedule. If eligibility criteria are not met in time to receive additional therapy during the course in which the toxicity occurred, but are met in time to start the next course (i.e., day 1 of the next course +/- 7 days), treatment will resume at 50% of the dose that caused the DLT. If toxicity again requires treatment cessation, treatment can be restarted at 25% of initial treatment dose. If treatment at this reduced dose results in recurrence of DLT or significant non-DLT toxicity, treatment will be permanently discontinued.

Repeat lab testing will be done weekly until eligibility criteria are met, and treatment will begin at 50% of the prior dose. If after 4 additional weeks of testing, eligibility criteria still are not met, the subject will not be eligible for any additional treatment with the study agent responsible.

Subjects with Grade 4 toxicity related to protocol treatment (other than transient lymphopenia from hu14.18-IL2, see Section 5.3.3.g) will not receive additional protocol treatment during that treatment course. Patients experiencing Grade 4 neutropenia or leukopenia that lasts \leq 4 days; Grade 4 thrombocytopenia that can be corrected with platelet transfusion (see Section 10.2.1); or Grade 4 nausea, vomiting, anorexia or fatigue lasting less than 2 days, and resolves to meet eligibility criteria, may be eligible to receive continued study therapy (provided that all other criteria for continued treatment are met) at 50% of the dose received prior to the onset of this toxicity. Subjects with any other Grade 4 toxicity related to the protocol treatment will not receive additional protocol treatment during that course and will be withdrawn from the study. Subjects experiencing Grade 4 events that are clearly unrelated to the study treatment, last \leq 3 days, and improve to meet eligibility criteria, may be eligible to receive continued study therapy (provided that all other criteria for continued treatment are met) at 50% of the daily dose received prior to the onset of this toxicity.

[figure not shown]

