7.2 Clinical Assessment

The detailed schedules for treatment administration and clinical monitoring are included below in Tables 5, 6A, and 6B.

TABLE 5. CLINICAL ASSESSMENT FOR EACH TREATMENT COURSE

DAY	Base Line ²	Week 1						Weeks 2-4	Week 5 ¹
		1	2	3	4			8	29/1 ¹
Hu14.18-IL2		X	X	X					X
Complete history/PE	X								
Physical Exam		X	X	X					X ³
Adverse event assessment		X	X	X	X			X	X ³
Weight	X	X	X	X	X			X	X ³
Performance Status	X	X	X	X	X			X	X ³
Pregnancy Status	X								
ECG	X								
Tumor Assessment	X ⁶								X ⁴
Vital signs (T, BP, P, RR)	X	X ^{5,6}	X ^{5,6}	X ^{5,6}	X			X	X ³
CBC, diff, plts	X			X				X	X ³
AST, ALT, T bili, alk phos, alb, LDH, Na, K, Ca, Mg, Cr, BUN, CRP ⁷	X			X				X	X ³
Serum phosphate ⁸ and glucose ⁹	X			X				X	X ³
INR/PTT	X			X					X ³
Urinalysis	X								X ³
Hgb A1C, TSH	X								
HIV/HBsAg	X								
Head MRI or Head CT	X								
Biopsy	X ¹⁰								

¹ Day 29 of each course (+/- 7 days leeway to facilitate clinical scheduling) = day 1 of subsequent course.

² Baseline tests/exams, with the exception of laboratory assessments, may be performed on or before day 1 but must be performed ≤ 3 weeks prior to randomization. Laboratory assessments must be done ≤ 2 weeks prior to randomization.

³ These tests may be performed up to 1 week prior to initiating the next course of therapy, or day 22-29 of the present course if no more study therapy is to be administered.

⁴ Tumor assessments will take place at baseline and after Course 2. (Long-term follow-up will include further tumor measurements; see Table 8.) The assessment after Course 2 will be performed no earlier than day 8, but can be performed out to day 29 (+/- 7 days leeway to facilitate clinical scheduling), thus allowing adequate time to obtain biopsies of any questionably recurrent disease to determine if the subject is eligible to continue on study (see Section 5.3.1.3 for details regarding these biopsies). Baseline radiological evaluation will include CT scans of the chest, abdomen, and pelvis, and head MRI. Assessments after Course 2 and during long-term follow-up will include CT scans of areas of known prior disease. Other examinations can be performed as warranted clinically. Consistency will be maintained in the imaging modality used to measure tumor while patient is on study.

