7.4.2 Anti-hu14.18-IL2 antibody levels

Serum specimens will be obtained at the indicated times shown in Table 7A and cryopreserved. These will then be tested in ELISA assays currently in use (36) and now being developed to detect and quantitate antibody against the hu14.18-IL2 IC molecule.

TABLE 7A.
IMMUNOLOGICAL AND PHARMACOKINETIC ASSESSMENT

	Base Line ¹	Week 1				Week 2	Week 5
DAY		1 ²	2	3	4	8	29(1) ^{2,3}
Hu14.18-IL2		X	X	X			
Serum hu14.18-IL2 levels ⁴		X/X	X/X	X/X			
Soluble IL2 receptor	X	X/C1		X/C1	X	X	X
Anti- hu14.18-IL2 Ab	X	X/C1		X/C1	X	X	X
Red top tubes (mL) ⁴	2x10	2x10/1x10; 3x10	1x10/1x10	2x10/1x10	1x10	1x10¹¹	1x10¹⁰
In vitro NK/ADCC studies ⁵	X					X C2+3	X C2+3
Green top tubes (mL) ⁵	1x10					1x10 C2+3	1x10 C2+3
In vitro T cell studies ^{6,7}	X^{6,7}						X^{6,7} C2+3
Heparinized syringe (mL) ^{6,7}	50						50^{6,7} C2+3
In vivo binding ⁸	X				X		

X/ = pre-IC⁹

/X = post-IC⁹

¹ Studies scheduled for “Baseline” can be obtained at any time from 3weeks prior to randomization until just prior to (within 10 minutes) beginning study treatment.

² Day 29 of each course (+/- 7 days leeway to facilitate clinical scheduling) = day 1 of subsequent course.

³ These tests may be performed up to 1 week prior to initiating the next course of therapy (day 22-29 of current course).

⁴ To better understand the pharmacokinetics of hu14.18-IL2 serum will be obtained from subjects in both groups for all courses to measure hu14.18-IL2 levels at the following times: pre and post the 4 hr IC infusion and again 2, 4, and 8 hours after completion of the 4-hr IC infusion on days 1 and 3; on day 2, only the pre- and post-IC samples will be collected.

- ⁵ *In vitro* testing of NK and ADCC function will be performed on selected patients five times with 10 mL of heparinized blood: at baseline, on day 8 of Courses 2 and 3 (C2+3) and within one week of the end of Courses 2 and 3. Additional lymphocytes obtained at the day 8 time points will be cryopreserved for subsequent DNA analyses.
- ⁶ Lymphocytes will be cryopreserved for subsequent T cell function testing from 50 mL of heparinized blood. Plasma collected with this sample also will be cryopreserved for subsequent immunological assays. This sample will be obtained three times: once at baseline, and within one week of the end of both Courses 2 and 3 (C2+3).

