10.1.1 Dose modification for DLT

Dose limiting Toxicity (DLT) criteria and exclusions are described in protocol section 5.3. For any occurrence of DLT, treatment with protocol therapy will be stopped. Treatment may not be resumed until after toxicity has resolved to meet original eligibility criteria. Resuming treatment following any DLT at a reduced dose (according to the guidelines below) requires contact (by phone or e-mail) with the FDA on a case-by-case basis. The first contact will be to the FDA Oncology Drug Products review division in the Center for Drug Evaluation and Research at [contact]. An alternate contact is at the following: [contact]; [contact], [contact].

For toxicities occurring during treatment with hu14.18-IL2, if DLT occurs on day 1 or 2 of any course, treatment can only be resumed during that same course (i.e., on day 2 or 3) at 50% of the starting dose, and only if the toxicity has resolved to meet eligibility criteria in time to give the day 2 or day 3 dose on schedule. If eligibility criteria are not met in time to receive additional therapy during the course in which the toxicity occurred, but are met in time to start the next course (i.e., day 1 +/- 7 days), treatment will resume at 50% of the dose associated with the DLT. Any planned drug administration that is withheld due to DLT will not be given on a delayed schedule to “make up” for missed drug. If toxicity again requires treatment cessation, treatment can be restarted at 25% of initial treatment dose. If treatment at this reduced dose results in recurrence of DLT or significant non-DLT toxicity, treatment will be permanently discontinued. Treatment will be resumed, as described above, using only 50% of the starting dose of hu14.18-IL2, and only if the toxicity has resolved to meet eligibility criteria.

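### Section 5.3 lets a hu14.18-IL2 course start up to 7 days early, but Sections 5.2.1 and 5.2.2 bar any start before 4 weeks

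*Combined protocol and SAP*

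**What the plan says.** **The floor.** Section 5.2.1 (Group A) states: "No course of hu14.18-IL2 therapy will be administered sooner than 4 weeks after day 1 of the prior course". Section 5.2.2 repeats the sentence for Group B. Neither gives an exception. The Schema text restates the minimum for Group A Course 2.

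**The leeway.** Section 5.3 sends the first course after surgery back to Section 5.2. It then says that Courses 1-3 in Group B and Courses 2-3 in Group A "will be repeated every 28 days (+/- 7 days to allow for scheduling constraints) at the same dose". Schema footnote 2 has "Each treatment cycle is 4 weeks (+/- 7 days" with no lower limit. Table 5 footnote 1 and Table 7A footnote 2 share one wording: "Day 29 of each course (+/- 7 days leeway to facilitate clinical scheduling) = day 1 of subsequent course".

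**After a toxicity.** Sections 5.4.4.1 and 10.1.1 also mention 7 days either side, but as a check on recovery. They ask whether the eligibility criteria "are met in time to start the next course (i.e., day 1 of the next course +/- 7 days" (5.4.4.1) or "are met in time to start the next course (i.e., day 1 +/- 7 days" (10.1.1).

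**The nominal interval.** Section 1.5.1 says "The 3-day administration schedule will be repeated on a 4-week interval". Sections 1.3.5 (Phase I experience), 2.2.1 and 8.1.1 likewise use 4 weeks or 28 days.

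**The concern.** Both statements are operative dosing rules for an investigational drug, and they give opposite answers for an early start. A team that uses the minus side of the window follows 5.3 and breaches 5.2. The same dose could then be logged as compliant by one person and as a deviation by another. At stake are the shortest re-dosing interval that the protocol really allows (21 or 28 days) and a consistent deviation record.

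**Working it through.** There is no plan figure to reproduce. The check is day arithmetic and a comparison of texts.

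**Inputs.** Floor: 28 days from the prior day 1 (5.2.1, 5.2.2). Window: 28 days, 7 either way (5.3), or day 29, 7 either way (Table 5 footnote 1). Planned subjects: 8 per group, 3 courses each (5.1, 5.3). Dose: 6 mg/m² on 3 days per course (5.3).

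**Start days**
- Earliest under 5.3: 29 − 7 = day 22, which is 21 days after the prior day 1.
- Latest under 5.3: 29 + 7 = day 36.
- Days in the window: 36 − 22 + 1 = 15.
- Days barred by 5.2: days 22-28, which is 7 days (21 to 27 days after the prior day 1).
- Days that satisfy both rules: 15 − 7 = 8 (days 29-36).

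**Which intervals carry both rules**

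| Interval | 28-day floor | −7 days under 5.3 |
|---|---|---|
| Group B, Course 1 to 2 | yes (5.2.2) | yes |
| Group B, Course 2 to 3 | yes (5.2.2) | yes |
| Group A, Course 2 to 3 | yes (5.2.1) | yes |
| Group A, Course 1 to 2 | yes (5.2.1, Schema) | no; 5.3 refers it to 5.2 |

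With three courses for everyone, Group B gives 8 × 2 = 16 intervals and Group A gives 8 × 1 = 8. That is 24 of 16 × 2 = 32. This counts where both rules apply; it does not predict breaches.

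**Largest compression.** If Group B used the full minus side twice, day 1 of Course 1 to day 1 of Course 3 would be 2 × 21 = 42 days. The floor requires at least 2 × 28 = 56.

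**Total planned dose.** 3 courses × 3 days × 6 = 54 mg/m² under either rule.

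**Can the floor be read as a surgical rule only?** In Group A, surgery falls on days 10-17. Adding 14 days for non-extensive surgery gives days 24-31, so a day-29 floor does real work there. But the sentence covers every course, and it also stands in 5.2.2. In Group B surgery comes before Course 1, so the floor can concern only Courses 1 to 2 and 2 to 3. Those are the intervals to which 5.3 gives −7 days.

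**Why Group A Course 1 to 2 needs its own rule.** Extensive surgery on days 10-17 plus 21 days gives days 31-38. Surgery on day 16 or 17 puts the earliest start on day 37 or 38, so a day-36 limit cannot apply to that interval.

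**The case against.** **The rules can be met together.** The floor is absolute and the leeway is permissive, so any start on days 29-36 satisfies both. This is true, and nothing suggests that early starts are planned. But the minus side then has no effect, and the text should say so.

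**The direction of the fix is a choice.** Lowering the floor to 3 weeks would also remove the conflict, and the documents do not state the intent. That stands. Keeping the floor is the cautious choice. A clause making 5.3 subject to the minimum in 5.2 would have the same +7/−0 effect.

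**Three stronger readings are tempting and are not supported.**
- *An early start spoils the end-of-course samples.* Table 7A footnote 3 says "These tests may be performed up to 1 week prior to initiating the next course of therapy (day 22-29 of current course", and a reader might infer that after a day-22 start most of days 22-29 would be post-dose. The rule, however, is the week before the next course actually starts, so the samples move with that start. The bracketed days describe the nominal schedule. Table 5 footnote 3 shows the same logic: it uses days 22-29 when no further course will follow.
- *Sections 5.4.4.1 and 10.1.1 set the same conflicting interval.* Their 7 days are anchored to day 1 of the next course and test recovery from toxicity. They do not set a time since the prior course.
- *A 21-day interval is unsafe or contradicts the rationale.* A nominal 4-week cycle in 1.3.5, 1.5.1, 2.2.1 and 8.1.1 is compatible with a tolerance. The protocol reports a serum half-life of 3.7 hours (1.3.5) and about 10% or less of the drug left after 24 hours (1.5.1). Retreatment also depends on toxicity recovery (5.3.1.1), a documented complete response before Course 3 (5.3.1.2), and FDA contact before resuming after a DLT (10.1.1). None of these sets a minimum interval, but the documents do not show that days 22-28 carry more risk.

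**Conclusion.** The contradiction is real. For Group B Courses 1 to 2 and 2 to 3, and Group A Course 2 to 3, a start on days 22-28 is both permitted and forbidden, and the documents give no order of precedence. The effect is confined to the re-dosing interval and to whether a dose counts as compliant. It arises only if the minus side is used. The count of 24 of 32 intervals assumes 8 subjects per group who all receive three courses. Total dose, sample size, power and the histology comparison are untouched. This is a minor correction, worth making because the rule governs dosing and the wording is easy to repair.

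**What to change.** Keep Sections 5.2.1 and 5.2.2 and the Schema text for Group A as they are. Then:

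1. In 5.3, change the leeway to *28 days (+7/−0 days; next day 1 on day 29-36)*.
2. Make Schema footnote 2, Table 5 footnote 1 and Table 7A footnote 2 match. Add *for Group A Course 1 to 2 see 5.2.1*, with no day-36 cap on that interval.
3. In 5.4.4.1 and 10.1.1, leave the wording and add only *subject to the minimum interval in 5.2*.
4. Leave the longer-delay rules unchanged: up to 3 weeks after a biopsy (5.3.1.3), 4 additional weeks of retesting (5.4.4.1), and up to 8 weeks for anemia (7.7).

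The cost is a wording amendment to four statements and two cross-references. The scheduling window falls from 15 to 8 days (7/15 = 47% fewer start days), and a course can no longer be brought forward, for example for bed or staff availability.
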